1.5.2 Long-Term Safety Outcomes

Additional, longer-termed, safety outcomes will be assessed by monitoring clinical data including:

- Changes in best spectacle corrected visual acuity
- Peripheral anterior synechiae (PAS)
- Cornea endothelial cell count
- Slit lamp findings
- Corneal thickness (Pachymetry)
- Visual field
- Fundus findings
- Other gonioscopic findings additional to PAS
- Adverse events
- Procedure-related complications

1.5.3 Adverse Events

All adverse events will be summarized, tabulated, and analyzed by:

- Seriousness
- Severity
- Outcome
- Relationship to the study device
- Relationship to the study procedure.

1.6 Study Population

Effectiveness endpoints for this study will be:

- The proportion of subjects with an IOP reduction of 20% or more from baseline at each postoperative visit.
- The proportion of subjects with an IOP reduction of 20% or more from baseline after 6 months while using the same number or fewer medications.

1.7 Study Population

1.7.1 Inclusion Criteria

The study eye must meet all the criteria below:

- Diagnosis of primary open-angle glaucoma (including pigmentary and pseudoexfoliative glaucoma).
- 2. Glaucomatous visual field defects consistent with optic nerve defects and defined as one or more of the following:
 - A cluster of 3 or more points in an expected location of the visual field depressed below the 5% level, at least 1 of which is depressed below the 1% level on the pattern deviation (PD) plot; or
 - b. Glaucoma hemi-field test "outside normal limits"

Note: Visual field reliability indices (i.e., fixation losses, false positives, and false negatives) should all be less than 33%. For subjects with a screening visual acuity of 20/100 or worse, a visual field is not required, and the above criteria do not need to be met.

- 3. Nerve abnormality characteristic of glaucoma as evaluated by clinical ophthalmoscopy defined as one or more of the following:
 - a. Diffuse thinning, focal narrowing or notching of the optic disc rim especially at inferior or superior poles.
 - b. Localized abnormalities of the peripapillary retinal nerve fiber layer, especially at inferior or superior poles.
 - c. Optic disc neural rim asymmetry of the two eyes consistent with loss of neural tissue.
- 4. Subject eye is phakic
 - a. If **phakic**, then the crystalline lens will not have visually significant cataract that is expected to require cataract surgery within next one year. Cataract will be evaluated by using the AREDS clinical lens grading system (ARLNS). Specifically, crystalline lens must have ARLNS grade of ≤ 1.5 for signs of nuclear opalescence, cortical or posterior subcapsular opacities. Lenticular opacities not characterized by the ARLNS grading system shall also be evaluated (e.g. anterior subcapsular cataracts).
- 5. Mean IOP with medication at screening between 21 mmHg and 35 mmHg, inclusive.
- 6. Iridocorneal angle anatomy defined as follows:
 - a. Trabecular meshwork visible on gonioscopy defined by Shaffer grade \geq 3.
 - b. Normal anatomy as determined by gonioscopy.
- 7. Light perception or better in the study eye at screening.

Note: The non-study eye must not have a Snellen corrected visual acuity (CVA) of worse than 20/200 at screening.

8. Age 45 years or older

- 9. Available, willing, with sufficient cognitive awareness to comply with examination procedures and schedules.
- 10. Signed written informed consent.

1.7.2 Exclusion Criteria

The study eye must not meet any of the criteria below:

- 1. Previous glaucoma surgeries including stent implantation or other laser surgeries on study eye.
- 2. Prior intraocular surgery.
- 3. Glaucoma types as follows:
 - a. Traumatic, uveitic, neovascular, or angle-closure.
 - b. Glaucoma associated with vascular disorders.
- Corneal status as follows:
 - a. Any condition that would preclude safe participation in the study or reliable IOP assessments including active inflammation, edema, keratitis, keratoconjunctivitis, keratouveitis.
 - b. Clinically significant dystrophy such as bullous keratopathy or Fuch's dystrophy.
 - c. Guttata that would preclude safe participation in the study or reliable study assessments.
 - d. Anticipated surgery of any type (including LASIK, LASEK, PRK, cataract, etc.) during the study that may alter IOP measurement.
 - e. Corneal opacities or disorders that would inhibit visualization of the angle (such as severe arcus senilis).
 - f. Central corneal thickness less than 440 microns or greater than 620 microns.
- 5. Choroid status as follows:
 - a. Choroidal detachment
 - b. Effusion
 - c. Choroiditis
 - d. Neovascularization
 - e. Any active choroidopathy.
- 6. Retinal or optic nerve disorders, either degenerative or evolutive, that are not associated with the existing glaucoma condition including: proliferative diabetic retinopathy, central retinal artery occlusion, central retinal vein occlusion, wet age-related macular degeneration, dry age-related macular degeneration (e. g., presence of numerous large drusen associated with disturbance to or elevation of the retinal pigment epithelium), significant retinal pigment epithelial changes or optic atrophy, pathological myopia, red disease.

Note: Minor diabetic retinopathy or hypertensive retinopathy are permitted.

7. Elevated episcleral venous pressure associated with:

- a. Active thyroid orbitopathy.
- b. Cavernous sinus fistula.
- c. Sturge-Weber syndrome.
- d. Orbital tumors.
- e. Orbital congestive disease.

8. Other ocular conditions as follows:

- a. Sequelae from trauma that would preclude safe participation in the study or reliable study assessments (e.g., chemical burns, blunt trauma, etc.)
- b. Chronic ocular inflammatory disease or presence of active ocular inflammation or infection (e.g., uveitis, iritis, iridocyclitis, retinitis)
- c. Any pathology for which, in the investigator's judgement, the following would be either at risk or contraindicated:
 - i. Compliance to elements of the study protocol (e.g., ophthalmic examinations, follow- up visits)
 - ii. Subjects with inadequate space in the anterior chamber and/or angle as determined by slit lamp examination and gonioscopy.

9. Subject status as follows:

- a. Uncontrolled systemic disease (e.g. diabetes, hypertension) that could compromise their participation in the study.
- b. Use of systemic medications (either current, within 30 calendar days of screening exam, or anticipated) that may cause an increase in IOP, (e.g. systemic steroids including oral or IV formulation, topical steroids applied on the periorbital surface within ¼" of the external lid margins and oral inhaled steroids). Nasal inhaled steroids are allowed.
- c. Active concurrent enrollment in any investigational trial or previous participation in any investigational trial within 30 days of the screening exam.
- d. Women who are nursing, are pregnant or are of childbearing potential who refuse to use reliable contraception.

STUDY MATERIALS AND METHODS

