1.1.2 Study Architecture

Study Architecture	
Study Design	This is a prospective, single-center, and single arm clinical trial of ViaLase Laser for the treatment of primary open angle glaucoma. Subjects will be screened for qualification as per the inclusion/exclusion criteria and must meet the inclusion/exclusion criteria in at least one eye to be enrolled. Up to 20 subjects will be consented as per the informed consent process. Subjects will be treated with the ViaLase Laser in one eye and followed for up to 12 months.
	Subjects will be screened for eligibility and informed consent will be obtained from consecutive subjects who meet screening criteria and are willing to participate in the study. Eligible subjects will be examined preoperatively to obtain a medical history and to establish a baseline ocular condition. Baseline and postoperative measurements will include distance visual acuity, manifest refraction, diurnal intraocular pressure, slit-lamp examination, gonioscopy, visual field, dilated fundus examination, specular microscopy, and pachymetry.
	Patient will continue use of IOP-lowering medications prior to surgery and up to 1 month post-operatively. The investigator has discretion to add, continue or remove medication thereafter.
	This study is being conducted in accordance with good clinical practice (GCP). Protocols have been submitted to and approved by an Ethics Committee for a study in patients freely providing informed consent. Data reporting, adverse event reporting and data collection is described in this protocol.
Study Location	Semmelweis University, Budapest, Hungary

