1.4 Study Design

This is a prospective, single-center, and single arm clinical trial of ViaLase Laser for the treatment of open angle glaucoma. Subjects will be screened for qualification as per the inclusion/exclusion criteria and must meet the inclusion/exclusion criteria in at least one eye to be enrolled. Up to 20 subjects will be consented as per the informed consent process. Subjects will be treated with the ViaLase Laser in one eye and followed for 12 months.

Eligible subjects will be examined preoperatively to obtain ocular and medical history and to establish a baseline ocular condition. Baseline and postoperative measurements will include distance visual acuity (best corrected), manifest refraction, intraocular pressure (IOP at baseline, 6 months and 12 months required), slit-lamp examination, gonioscopy, visual field, dilated fundus examination, specular microscopy (at baseline, 6 months and 12 months), and pachymetry.

Subjects who are on IOP lowering medications will be allowed to continue prior to laser treatment and up to one-month post-treatment. It is the investigator's discretion whether to add, continue or stop the medications after one month.

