3.3 Postoperative Instructions

Refer to Appendix B for complete instructions associated with Methods of Clinical Evaluation.

- 1. Following surgery, the investigator or designee will instruct subjects to adhere to the following antibiotic/anti-inflammatory medication regimen for the study eye only:
 - a. Topical antibiotic that is utilized as investigator's routine postop regiments.
 - b. Continuation of glaucoma medications.
- During the study, the discontinuation or a reduction in the dose or frequency of topical IOP lowering medication may be warranted whenever it is in the interest of patient safety.
 Conditions that may warrant discontinuation or frequency reduction in medication include hypotonous condition, an adverse reaction, or other systemic side effect.
- 3. If a pressure rise is observed, a paracentesis may be performed, as necessary. If a paracentesis is performed and there is no protocol-defined adverse event, the paracentesis will be documented in the applicable clinical report form (CRF). If, however, the paracentesis is performed and an anticipated adverse event is determined, then the AE will be recorded, and the paracentesis will be recorded on the applicable CRF as a treatment for the AE.

3.4 Examination Schedule:

Follow-up visits (as shown in Appendix A) will be scheduled over the course of 6 months. A CRF will be completed for each scheduled, unscheduled, and interim exam. Scheduled visits are defined as visits outlined in the schedule of visits. Interim visits are defined as study related visits deemed necessary by the protocol or the PI that are in addition to scheduled visits, and unscheduled visits are defined as visits that are not scheduled or interim. Subjects will be examined and evaluated according to the following scheduled visits:

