3.7.2 Adverse events knowing to occur during or after laser procedures

Specific examples of adverse events that potentially may occur during or after laser surgery (regardless of likelihood) include but are not limited to:

- Choroidal hemorrhage
- Choroidal effusion
- Cyclodialysis cleft
- Significant hyphema (i.e. ≥ 10% of anterior chamber)
- Significant iris damage

Possible postoperative adverse events:

- Allergic reaction
- Intraocular inflammation (not pre-existing) remaining or arising after the protocol's specified medication regimen is complete
- Choroidal effusion
- Choroidal hemorrhage
- Aqueous misdirection
- Chronic pain in the study eye present greater than 3 months postoperative
- Clinically significant cystoid macular edema

- Corneal abrasion
- Flat or shallow anterior chamber (e.g., shallowing of the anterior chamber that causes any amount of iris-cornea touch)
- Hypotony (IOP < 6 mmHg) associated with clinically significant findings. (Clinically significant hypotony is defined as hypotony maculopathy or hypotony with flat anterior chamber requiring reformation, corneal folds, choroidal effusions requiring drainage, and/or suprachoroidal hemorrhage)
- Increase in C/D ratio of > 0.3 units
- IOP increase requiring management with oral or intravenous medications or with surgical intervention
- IOP increase ≥ 10 mmHg vs. baseline IOP occurring at any visit
- Iridodialysis
- Loss of best spectacle corrected visual acuity (BSCVA) of 2 lines or more (logMAR scale; 10 letters or more on ETDRS chart)
- Pupillary block
- Secondary surgical intervention
- Significant corneal complications including opacification and decompensation
- Significant corneal edema (NOTE: A classification of mild to moderate corneal edema up to and including the Week 1 postoperative exam is NOT considered an adverse event)
- Significant hyphema (≥ 10% of anterior chamber)
- Vitreous hemorrhage
- Worsening in visual field of mean deviation (MD) of ≥ 2.5 dB compared to the MD used to determine subject eligibility (confirmed in at least 2 out of 3 postoperative visual field tests performed within a 90-day period)

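### The 20% IOP responder rate and the mean IOP change carry no medication condition, so in this single-arm study a fall under an added or increased IOP-lowering drug counts as laser response; exclusion 9b closes only the IOP-raising direction

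*Combined protocol and SAP*

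**What the plan says.** **Entry.** Section 1.7.2, item 9b, excludes "Use of systemic medications (either current, within 30 calendar days of screening exam, or anticipated) that may cause an increase in IOP". Item 9a excludes "Uncontrolled systemic disease (e.g. diabetes, hypertension) that could compromise their participation in the study", so a subject with controlled hypertension can enter. Neither item mentions systemic drugs that lower IOP.

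**Medication during the study.** Section 1.1.2 states: "Patient will continue use of IOP-lowering medications prior to surgery and up to 1 month post-operatively". It continues: "The investigator has discretion to add, continue or remove medication thereafter". Section 1.4 repeats this: "It is the investigator's discretion whether to add, continue or stop the medications after one month". Neither section limits route or class. Section 3.3 (Postoperative Instructions), item 2, deals only with less treatment: a discontinuation or "reduction in the dose or frequency of topical IOP lowering medication may be warranted".

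**Endpoints and analysis.** Section 1.6 lists two effectiveness endpoints. The first is the proportion of subjects with at least a 20% IOP reduction at each postoperative visit, with no medication condition. The second applies after 6 months and adds "while using the same number or fewer medications". Section 3.9 is descriptive. It summarises IOP change, tallies the 20% responders at each visit, and separately tallies the number and frequency of medications. It does not link the tallies.

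**Data collected.** Appendix A schedules an ocular and a general medication assessment at Screening, Baseline and every postoperative visit, but not on Day 0.

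**The concern.** Item 9b protects the IOP results in one direction. Drugs that would push IOP up, and so work against the device, are kept out. Drugs that would push it down are not. Exclusion 4d, by contrast, bars anticipated surgery that may alter IOP measurement in either direction.

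An entry rule is only part of the matter. Once a subject is in the study, an IOP-lowering drug may be added at the investigator's discretion after Month 1, or a systemic drug may be started or increased for an unrelated reason. The first endpoint and the mean change then absorb its effect. There is no control arm in which the same drug use would show up, so nothing separates drug effect from laser effect, and the error runs in the device's favour.

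**Working it through.** The plan states no sample-size derivation, effect size, SD or success criterion, so there is no figure to reproduce. The check has two parts.

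**1. Which results are exposed**

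| Result | Medication condition | Exposed to |
|---|---|---|
| Endpoint 1, 20% responders at each visit (1.6, 3.9) | none | any added or increased IOP-lowering drug, topical or systemic |
| IOP change summaries (3.9) | none | the same |
| Endpoint 2, 20% responders after 6 months (1.6) | number of medications not above baseline | dose increases; new systemic drugs only if they are not counted |

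**2. Size**

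From the documents: entry IOP 21 to 35 mmHg (1.7.1, item 5), a 20% threshold (1.6), and up to 20 subjects (1.1.2).

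- Response threshold = 0.20 × baseline: 4.2 mmHg at 21, 5.0 at 25, 6.0 at 30, 7.0 at 35.
- Weight of one subject = 1/20 = 5 points.

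The documents give no size for a systemic drug effect. Assume 1, 2 or 3 mmHg. Divided by the threshold, the drug alone supplies 24%, 48% or 71% of the required fall at baseline 21 (1/4.2, 2/4.2, 3/4.2), and 14%, 29% or 43% at baseline 35. It would not usually make a responder by itself, but it can carry a partial laser effect over the line.

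Illustration, all values assumed: baseline 25, mean laser drop 3 mmHg, SD 3 or 4, normal model.

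P(response) = 1 − Φ((5 − 3 − drug drop)/SD)

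Expected shift = (number affected/20) × (P with drug − P without drug)

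| Drug drop (mmHg) | P, SD 3 | P, SD 4 | Shift, 1 affected (points) | Shift, 3 affected (points) |
|---|---|---|---|---|
| 0 | 0.252 | 0.309 | – | – |
| 1 | 0.369 | 0.401 | 0.5–0.6 | 1.4–1.8 |
| 2 | 0.500 | 0.500 | 1.0–1.2 | 2.9–3.7 |
| 3 | 0.631 | 0.599 | 1.5–1.9 | 4.4–5.7 |

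The range of 1 to 3 affected subjects corresponds to an assumed 5 to 15% of 20. With a 2 mmHg drug effect the expected shift is about 1 to 4 points. If the laser itself did nothing (mean drop 0), the same drug effect would give P rising from 0.048 to 0.159 (SD 3) or from 0.106 to 0.227 (SD 4), a shift of about 0.6 to 1.8 points for 1 to 3 subjects.

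**A related inconsistency.** Section 3.9 defines baseline as Day 0 before treatment, but Appendix A has Day 0 IOP taken after surgery and no medication assessment that day. If the Baseline visit supplies the reference value instead, a drug change in the 3 to 60 days before the laser also enters the IOP change. These passages must be reconciled before any rule on changes since baseline can work.

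**The case against.** The strongest reply is that the study's objective is initial evidence of safety. The IOP results are descriptive, with no test, margin or success criterion, and section 3.9 already tallies medications beside them. That stands: no error rate or power is affected. But the responder rate will still be read as the laser's effect, and a separate tally does not show which responders had a drug added.

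Four stronger readings are tempting, and the documents do not support them.

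- *That item 9b is the cause.* It is an entry criterion and cannot prevent an unforeseen start during follow-up. Rewording it alone would leave the main route open: added medication, topical included, combined with an endpoint that has no medication condition. Nor is an IOP-lowering drug plainly free to be started around the laser. Section 1.1.2 has such drugs continued up to Month 1 and gives discretion to add only afterwards, though it does not expressly bar an addition earlier.
- *That both responder endpoints are inflated by any new systemic drug.* The condition in endpoint 2 is not limited to ocular drugs, so a new drug could raise the count and make the subject a non-responder. What is open is whether systemic drugs count; a dose increase escapes in either case.
- *That IOP rises are hidden.* Section 3.7.2 lists "IOP increase requiring management with oral or intravenous medications or with surgical intervention" among possible adverse events, and section 3.7.1 has treatment of ocular events recorded. A drug taken for another reason might blunt a rise, but the documents give no basis for a size.
- *That the bias is 5 to 15 points.* This is a ceiling: it assumes 1 to 3 affected subjects and that every one of them crosses 20% only because of the drug.

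Some treatment sections are redacted, so the statement that nothing limits these drugs applies to the readable text only.

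**Conclusion.** The point holds in a limited form. Item 9b is one-sided. More importantly, endpoint 1 and the IOP change summaries count an IOP fall under any added or increased IOP-lowering drug as laser response, in a design with no control. Endpoint 2 is only partly exposed.

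The 5 points per converted subject is arithmetic on 20 subjects. The number of subjects affected, the drug effect, the laser effect and the SD are all assumptions. With 1 to 3 affected and a 2 mmHg drug effect, the expected shift is about 1 to 4 points, less than one subject in 20; over drug effects of 1 to 3 mmHg it runs from about 0.5 to 6 points. This is a modest bias in the device's favour, in descriptive results, and cheap to make visible.

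**What to change.** 1. **Section 3.9 (the main change).** Use the medication assessments already in Appendix A, with dose and date of change recorded, to flag every IOP value taken after any IOP-lowering drug, ocular or systemic, was started or increased since the baseline reference. Report the mean change and the 20% responder rates with and without the flagged values, for example with flagged values counted as non-response in the second responder summary, and give the number flagged. Neither summary is free of bias, so both should be shown. State that the medication count in endpoint 2 includes systemic IOP-lowering drugs. Reconcile the definition of baseline with the Day 0 schedule.
2. **Section 1.7.2, item 9b.** Add that any systemic IOP-lowering drug must be unchanged within the protocol's own 30-day period before Screening, with no change anticipated. Subjects on a stable dose remain eligible.

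Neither change alters what the investigator may prescribe.

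**Cost.** A few sentences and somewhat more detail in medication recording: the readable text mentions a medication list and a tally of number and frequency, not dose or change dates. There may be a few more screen failures, which count against the cap of 20 consented subjects and so could reduce the number treated.

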2.1 Device Description

The ViaLase Laser is a precision ophthalmic surgical device designed for the creation of trabecular apertures in the treatment of open angle glaucoma. The ViaLase Laser is like other commercially available surgical femtosecond lasers in ophthalmology that use focused femtosecond laser pulses to create incisions and separate tissue. The primary difference between the ViaLase Laser and other devices is a specialized optical delivery system that focuses light into the iridocorneal angle. Like other femtosecond lasers, the ViaLase Laser creates planes of micron-sized photodisruptions sites within a volume of tissue. An incision, aperture or canal is achieved by contiguously placed microphotodisruptions scanned by a computer-controlled delivery system.

This section has been redacted of company proprietary information

VIA-001 Rev. A

This section has been redacted of company proprietary information

This section has been redacted of company proprietary information

STUDY PROTOCOL

